11.1.4 Suspected unexpected serious adverse reaction (SUSAR)

A suspected unexpected serious adverse reaction (SUSAR) is an adverse drug reaction which both

- meets the definition of a serious adverse event
- is 'unexpected' in that the nature and severity of the event is not consistent with the applicable product information (i.e. Investigator's Brochure)
- Investigators will assess causality but do not assess expectedness, this is done by the nominated reviewer(s) on receipt of all SAEs. The reviewer will refer to the information supplied within the Investigator's Brochure and the CTR trial team will report events as SUSARs only if the nature, seriousness, severity and outcome is not consistent with the relevant product information.

The following events will be classified as **expected SAEs** related to CMML within this trial and therefore will not be reportable as SUSARs:

- Neutropenic sepsis
- Grade 4 haematological toxicity

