10.3 Independent Data Monitoring Committee (IDMC) and formal interim analysis

An Independent Data Monitoring Committee (IDMC) will review the accumulating safety and efficacy results of the trial on a continuous basis and a formal interim analysis will be performed after a sufficient number of evaluable patients have been treated to be able to determine whether the continuation criteria for progression to the second stage of the study have been met (see section 10.1). Recruitment to the study may thus need to be temporarily halted after the first 19 patients to allow sufficient safety and clinical efficacy data to accumulate. The IDMC will also have the power to request to suspend recruitment or stop the study at any time in the setting of emerging safety concerns. CTR will send safety and efficacy data, along with current recruitment figures to the IDMC whenever they are notified of a new treatment-related death or grade 3/4 non-haematological adverse reaction. To inform the decision of whether or not to proceed to the second stage of the study, overall response rates following completion of cycle 3 of tefinostat may be presented to the IDMC as an early indication of response. All analyses will be kept confidential until the end of the study.

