Although this was not statistically significant, it was still evident at the end of the 28-day recovery period. Clinical chemistry changes noted included increased total bilirubin (all dose levels), increased urea (females, all dose levels) increased asparatate aminotransferase, alanine aminotransferase and lactate dehydrogenase (450 mg/kg/day), decreased cholesterol (150 and 450 mg/kg/day) and increased creatinine (150 and 450 mg/kg/day). Decreased thymus weight was apparent at the end of the treatment period for all dose levels and was still evident at the end of the 28-day recovery period for females. Moderate or marked thymic atrophy was noted at 450 mg/kg/day with mild atrophy evident for individual animals dosed at 50 and 150 mg/kg/day. This finding was still evident in females at a reduced severity on completion of the 28-day recovery period. Accumulation of haemosiderin (mild or moderate) in Kupffer cells was present in the liver of animals treated at 450 mg/kg/day and females at 150 mg/kg/day with minimal accumulation observed sporadically in the remaining treatment groups. The finding was still evident in females at a reduced severity on completion of the 28-day recovery period. Minimal or mild centrilobular hepatocyte hypertrophy or minimal or mild hepatocyte degeneration was evident for individual animals at 150 and 450 mg/kg/day. These findings were not evident at the end of the 28-day recovery period. Mild periportal fatty vacuolation was observed at the end of the 28-day recovery period in one animal of each sex previously dosed at 450 mg/kg/day. A NOAEL could not be defined for this study.

Tefinostat appears to be devoid of mutagenic potential in bacteria and whilst it has been shown to induce a higher than control incidence of chromosomal aberrations in cultured CHO cells, this is only apparent at concentrations of 200 and 210 μ g/mL (in the presence of S9 mix) which are toxic to the test cells.

The data suggest that subjects entered into clinical studies should be carefully monitored for evidence of haematological toxicity.	

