APPENDIX 12: SUMMARY OF CLINICAL INFORMATION GUIDANCE FOR THE INVESTIGATOR

Tefinostat is an orally-delivered histone deacetylase inhibitor targeted towards cells of the myelomonocytic lineage. Tefinostat was administered to humans for the first time in an open, uncontrolled, Phase I study. Cohorts of cancer patients with advanced or treatment refractory haematological diseases were administered increasing dose levels of tefinostat with the primary aim of assessing the safety and tolerability of the drug and finding a suitable dose and dosing regimen for future clinical studies.

The demographic characteristics of the patients suggest that they were broadly consistent with the patient group typically seen in clinical practice. The median age was 72 years (range 50 - 79). Eighteen patients entered the trial and all 18 patients completed at least the first 28-day cycle of treatment. The most common disease in this study was AML. There were four patients with diseases which might be expected to be driven by cells of the myelomonocytic lineage: two CMML patients and two AML-M5 patients.

Dose escalation followed steps of 100%, starting at 20 mg daily. There were no DLT during the study and dose escalation continued until the once-daily dose reached 640mg. This dose required patients to take 8 x 80 mg capsules and potential problems with patient compliance prevented any further dose escalations. In addition, there were early signs in the safety and pharmacodynamic data (increased plasma creatinine and decreased specificity of monocyte-targeting) that the dose of 640mg CHR-2845 resulted in exposure of levels of drug in tissues outside the hCE-1 expressing compartment that were capable of inhibiting HDAC. No MTD or MAD were identified in this study because dose escalation was halted prior to observation of DLT.

Dose-limiting toxicities that have been seen after exposure to non-targeted histone deacetylase inhibitors (e.g., fatigue, gastrointestinal toxicity, thrombocytopenia) were not seen after treatment with tefinostat, indicating that the targeted nature of the drug is able to provide maximal pharmacodynamic activity in the absence of significant toxicity.

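### Section 11.1.4 exempts tefinostat-attributed neutropenic sepsis and grade 4 haematological toxicity from SUSAR reporting on disease grounds, against its own product-information test and section 11.3

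*Protocol*

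**What the plan says.** Section 11.1.4 of the protocol defines a SUSAR as a drug reaction that is serious and that "is 'unexpected' in that the nature and severity of the event is not consistent with the applicable product information", naming the Investigator's Brochure as that information. It then lists two event types, "Neutropenic sepsis" and "Grade 4 haematological toxicity", as expected events "related to CMML within this trial and therefore will not be reportable as SUSARs". The list carries no condition on suspected cause.

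Section 11.3 has the reviewer judge expectedness for every SAE and serious adverse reaction, and classes an unexpected serious adverse reaction as a SUSAR. Section 11.5 sets the clock: 7 days for fatal or life-threatening SUSARs, 15 days for the others, and an annual report for all SAEs and serious adverse reactions.

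Section 10.3 has the trials centre send data to the IDMC "whenever they are notified of a new treatment-related death or grade 3/4 non-haematological adverse reaction". Appendix 11 closes its non-clinical summary with: "The data suggest that subjects entered into clinical studies should be carefully monitored for evidence of haematological toxicity".

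**The concern.** Section 11.1.4 contains two tests of expectedness. The definition asks whether the event is known for the drug. The list answers by asking whether the event is known in the disease. For a cytopenia or a neutropenic infection in CMML the two answers can differ, and the section does not say which prevails when the investigator suspects tefinostat.

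At stake is the speed and independence with which a suspected drug effect on the marrow reaches the regulator and the IDMC. Prior exposure is thin: section 4.1 gives two CMML patients among the 18 treated in phase I. Eligible CMML-1 patients may enter with platelets below 50 x 10⁹/l or red cell transfusion dependence (section 5.1). Disease and drug effects will therefore be hard to separate, which is a reason for an explicit rule.

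**Working it through.** No arithmetic applies; the check sets the rules side by side.

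**Step 1: what the exemption can act on.** There are two readings of the list.
- If it covers all events of the two types, it removes those suspected to be caused by tefinostat.
- If the reference to CMML limits it to disease-caused events, it has no effect, because an event not suspected to be a drug reaction cannot be a SUSAR under the section's own definition.

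The list therefore either does nothing or exempts suspected drug reactions.

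**Step 2: whether the protocol's safety information makes the events expected for the drug.** Section 11.4 points to section 2.3.3, Appendices 11 and 12, and the Investigator's Brochure. Section 2.3.3 and Appendix 12 give the at least possibly related events as nausea, anorexia, rash, fatigue, constipation and raised creatinine. Appendix 12 gives the related SAEs as PR prolongation, mucosal inflammation, asthenia, anorexia and confusional state. Neither exempted event appears. The Brochure cannot be checked here.

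**Step 3: which rules reach a related, non-fatal event.**

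| Rule | Section | Grade 4 haematological toxicity | Neutropenic sepsis |
|---|---|---|---|
| 7/15-day SUSAR report | 11.1.4, 11.5 | exempt | exempt |
| Event-driven IDMC mailing | 10.3 | not covered | grade 3/4 covered only if classed as non-haematological |
| Primary safety endpoint and limits (6 or fewer of 19; fewer than 13 of 40) | 10.4.1, 10.1 | not counted | grade 3-4 in cycles 1-2 counted only if classed as non-haematological |
| SAE report within 24 hours, with causality | 11.1.3, 11.2.2 | yes, if a general seriousness criterion is met | the same |
| Continuous IDMC review, including all reported SAEs | 10.3, 11.5 | yes | yes |
| Immediate notice to MHRA and REC | 11.5 | if judged a significant safety issue | the same |
| Annual report | 11.5 | yes, if reported as an SAE | the same |
| Patient-level rule for related grade 3-4 toxicity | 7.6.1 | yes | yes, at grade 3-4 |

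The protocol does not say whether neutropenic sepsis is haematological. Section 11.1.4 lists it as a separate item.

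**Step 4: result.** The first two rows are the expedited trial-level triggers tied to single events. Neither applies to related, non-fatal grade 4 haematological toxicity. The SUSAR route is also closed to related neutropenic sepsis, and the IDMC mailing is closed to it if it is classed as haematological. The remaining routes are open, but they depend on judgement, on periodic review, or act on the individual patient.

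**The case against.** The strongest counter-case is that the protocol is far from blind to these events, and most of it stands. Blood counts are taken fortnightly in cycles 1-6, and all adverse events are graded. Serious ones reach the trials centre within 24 hours with a causality opinion, and a clinical coordinator reviews each. The IDMC sees all reported SAEs and may ask to suspend or stop. A reader might infer from section 11.1.4 that no rule would flag drug-induced marrow toxicity, or that it would surface only in annual reports and routine tables. The documents do not support either inference.

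Four further points limit the finding.
- **The Brochure is unseen.** If it lists these events as expected for tefinostat, the exemption is redundant; if it does not, the exemption overrides it. The related-event lists in section 2.3.3 and Appendix 12 are also not stated to be complete.
- **Appendix 12 must be read narrowly.** Its statement that "fatigue, gastrointestinal toxicity, thrombocytopenia) were not seen after treatment with tefinostat" concerns dose-limiting toxicities of non-targeted agents. It does not show that thrombocytopenia never occurred.
- **The animal findings are modest.** The anaemia was reversible and regenerative, platelets rose at the two higher monkey doses, and the lymphocyte fall was not statistically significant. Appendix 11 asks for haematological monitoring but does not rank it as the main signal.
- **Fatal cases are partly covered.** A treatment-related death prompts an IDMC mailing at any time and counts in the primary endpoint if it falls in cycles 1-2. Whether fatal haematological toxicity falls under the grade 4 item is unclear.

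Leaving disease-confounded cytopenias out of the toxicity endpoint is a defensible choice in this population and is not criticised here. None of these points resolves the conflict within section 11.1.4 or restores the expedited report.

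**Conclusion.** The rule is wrong as written. Section 11.1.4 replaces a drug-based test of expectedness with a disease-based one, and so conflicts with its own definition and with section 11.3.

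Within the two listed categories, every serious event suspected to be caused by tefinostat loses the 7- or 15-day report. How many events that means cannot be stated, because the documents give no frequency. A grade 4 cytopenia that meets no seriousness criterion is unaffected, since it could not be a SUSAR in any case.

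The conclusion on SUSAR reporting rests on the text alone. The gap in the IDMC mailing is certain for non-fatal grade 4 haematological toxicity. For neutropenic sepsis it holds only if that event is classed as haematological. No endpoint, boundary or sample size is affected. Given the remaining safeguards, this is a correction to safety reporting of moderate weight and not a failure of safety oversight.

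**What to change.** 1. **Section 11.1.4:** limit the exemption to neutropenic sepsis and grade 4 haematological toxicity judged not related to tefinostat. State that related cases have their expectedness assessed against the Investigator's Brochure like any other serious adverse reaction, consistent with section 11.3. The list then only clarifies what the SUSAR definition already implies.
2. **Section 10.3:** add related grade 4 haematological toxicity and related neutropenic sepsis to the events that make the trials centre send data to the IDMC. Naming both removes the need to settle how neutropenic sepsis is classed for this purpose.

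The primary safety endpoint and both stopping limits stay unchanged. Causality is already collected for SAEs (section 11.2.2), so the cost is protocol wording, a few more expedited reports and a few more IDMC mailings.

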11.2 Adverse event reporting requirements

11.2.1 Adverse events

Information about adverse events and reactions, whether volunteered by the patient, discovered by investigator questioning or detected through physical examination, laboratory test or other investigation will be collected and recorded for all patients from the time of start of protocol treatment until 30 days after the last dose of tefinostat therapy. All AEs should be captured on the Adverse Events Forms within the CRF. AEs will be reviewed using the Common Terminology Criteria for Adverse Events (CTCAE) version 4 (see Appendix 8). For each adverse occurrence, the highest grade observed since the last visit should be recorded.

11.2.2 Serious adverse events

SAEs should be monitored from the time of patient registration until 30 days following the last administration

of protocol treatment. On becoming aware that a patient has experienced an AE defined as serious (see

11.1.3), the event should be reported on a SAE form. The investigator (or delegate) must complete, date and

sign the form which should be emailed (or faxed if email is not possible) to CTR using the contact details listed

below within 24 hours of first becoming aware of the event. Please ensure that multiple events are not

combined into one SAE form.

SAE Email: [contact]

SAE [contact]

When completing the form, the investigator will be asked to define the causality and severity of the SAE which

should be documented using CTCAE version 4. They will not be asked to define expectedness, this will be

carried out by the clinical reviewer.

It is accepted that a causality assessment is not always available at the time of the initial report – this opinion

should be provided as soon as possible to ensure that regulatory reporting timelines are met.

Investigators should also report SAEs to their own Trust in accordance with local practice. All SAEs should be

followed up until resolution or stabilisation of the event.

11.3 Trials office

CTR will assign each SAE a unique reference number which should be quoted on all correspondence and

follow-up reports regarding the SAE. On receipt of an SAE form by CTR, seriousness and expectedness will be

determined independently by a Clinical Coordinator (the Chief Investigator or his nominee). An SAE judged by

the local investigator to have a reasonable causal relationship to the trial medication will be regarded as a

Serious Adverse Reaction (SAR). The reviewer will assess all SARs and SAEs for expectedness. If the event meets

the definition of a SAR that is unexpected it will be classified as a SUSAR.

11.4 Reference Safety Information

An overview of the current clinical experience and safety information pertaining to tefinostat is provided in

section 2.3.3 of this protocol. More detailed summaries of pre-clinical and existing clinical information relating

to tefinostat can be found in appendices 11-12 and in the latest version of the tefinostat investigator's brochure.

11.5 Reporting to the regulatory authorities

CTR will report a minimal data set of all individual events categorised as fatal or life-threatening SUSARs to the MHRA, the main Research Ethics Committee (REC) and the sponsor within 7 days. Detailed follow-up information will be provided within an additional 8 days. All other events classified as SUSARs will be reported within 15 days.

CTR will report details of all SAEs and SARs (including SUSARs) to the MHRA and main REC annually from the date of Clinical Trial Authorisation, in the form of a Development Safety Update report. Details of all AEs can be reported to the MHRA on request.

The MHRA and main REC will be notified immediately if a significant safety issue is identified during the course of the trial.

Details of all SUSARs and any other safety issues which arise during the course of the trial will be reported to Principal Investigators. A copy of any such correspondence should be filed in the ISF.

The independent Data Monitoring Committee (DMEC) will assess toxicity (including all reported SAEs) as described in section 10.3

11.6 Deaths

Deaths must be reported as an SAE within 24 hours of becoming aware of the event if they meet the criteria outlined in 11.1.3 above. The date and cause of death will be collected. All deaths must also be recorded on the death report form, this information will also be collected in trial CRFs.

11.7 Pregnancies

Pregnancies occurring in study participants or participant's partners during tefinostat treatment or within 30 days of the last dose of study treatment may represent a safety issue. All pregnancies must be reported immediately to CTR using the pregnancy report form and, for pregnancies occurring in study participants, tefinostat treatment should discontinue.

Where a pregnancy is known, this should be followed for outcome and any adverse outcomes assessed for causality to the treatment received. There is a separate Patient Information Sheet and Informed Consent Version 3.0, 28/03/2017

Page 57 of 85

Form that should be completed by the pregnant person to give CTR permission to follow their pregnancy to outcome.

12 TRIAL GOVERNANCE AND ETHICAL CONSIDERATIONS

12.1 Clinical governance and Quality Assurance

The Monocle trial will be conducted according to the protocol and in compliance with the principles of Good Clinical Practice in clinical trials as described in the International Conference on Harmonisation Guidelines, including the archiving of essential documents (CPMP/ICH/135/95). The trial must also conform to local Research Governance procedures; sites will not be permitted to enrol patients until written confirmation of local R&D approval is received by CTR. Centres are required to complete a registration process with CTR before recruitment is started and to confirm acceptance of the terms of sponsorship required by Cardiff University. It is the responsibility of the Principal Investigator to ensure that all subsequent amendments gain the necessary local approval.

CTR will manage the trial and will follow unit SOPs with regard to the handling of substantial amendments, archiving and all other generic clinical trial activities. CTR and the sponsor have systems in place to ensure that there is reporting and appropriate action taken in respect of:

- Serious breaches of GCP, the trial protocol and the Clinical Trial Authorisation
- Urgent safety measures
- Protocol violations

Investigators are required to promptly notify CTR if they become aware of a trial-related serious breach of GCP and/or the trial protocol. It is also the responsibility of individual clinicians to take immediate action if thought necessary to protect the health and interest of individual patients.

A 'serious breach of GCP' is defined as a breach which is likely to effect to a significant degree:

- The safety or physical or mental integrity of the subjects of the trial; or
- The scientific value of the trial

For further information the Investigator should contact the Trial-coordinator at CTR.

12.2 Ethical considerations

The trial will be performed in accordance with the recommendations guiding physicians in biomedical research involving human subjects, adopted by the 18th World Medical Association General Assembly, Helsinki, Finland, 1964 and amended at the 48th World Medical Association General Assembly, Somerset West, South Africa, 1996. Informed written consent must be obtained from patients prior to registration into the study. The right of a patient to refuse participation without giving reasons must be respected. The patient must remain free to withdraw at any time from the study without giving reasons and without prejudicing his/her further treatment. The final study protocol, patient information sheets, consent forms and all other relevant study documentation will be submitted to and approved by a main Research Ethics Committee (Main REC) and the Medicines and Healthcare Products Regulatory Agency (MHRA) prior to circulation to sites and entering patients into the trial.

13 STUDY FINANCES

13.1 Funding sources

The Monocle trial is funded by Bloodwise.

Sixth Element Capital are supplying tefinostat free of charge for use in the study.

13.2 Patient expenses / payments

Participants will not receive payments for taking part in the Monocle study.

Patients will be able to claim reimbursement of any additional travel expenses and hospital parking costs that are incurred when attending Monocle study appointments that are considered over and above their routine care.

14 INSURANCE AND INDEMNITY

The Monocle trial is sponsored by Cardiff University. Cardiff University employees are indemnified by the University insurers for negligent harm caused by the design or co-ordination of the clinical trials they undertake whilst in the University's employment. Cardiff University cannot offer indemnity for non-negligent harm. Cardiff University is independent of any pharmaceutical company and, as such, is not covered by the Association of British Pharmaceutical Industry (ABPI) guidelines for patient compensation.

The NHS has a duty of care to patients treated at Trust and non-Trust hospitals, whether or not the patient is taking part in a clinical trial, and the NHS remains liable for proven clinical negligence and other negligent harm to patients under this duty of care.

